7 ANALYSIS SETS

7.1 Definitions of analysis sets

7.1.1 Screened analysis set

The Screened Analysis Set (SCR) includes all subjects who were screened and received a subject number.

7.1.2 Full analysis set

The Full Analysis Set (FAS) includes all randomized subjects.

In order to preserve the randomization, subjects will be evaluated according to the treatment they have been randomized to.

The main analyses of the primary and all secondary endpoints will be based on the FAS. For the efficacy analyses on the FAS, unless otherwise stated, all available efficacy data up to the EOS will be included.

7.1.3 Per-protocol analysis set / Per-protocol analysis

The Per-Protocol analysis (PP analysis) will be based on data from all subjects in the FAS not affected by major protocol deviations. Major protocol deviations are defined as protocol deviations that impact the assessment of the primary/secondary endpoints.

The Per-protocol Set (PPS) comprises all subjects included in the FAS without any major protocol deviations occurring prior to or at randomization. Due to the nature of the primary endpoint which is assessed over the entire study period rather than at a fixed time point, for subjects developing major protocol deviations during the study, only data collected after a major protocol deviation will be excluded from the PP analysis.

Subjects will be excluded from the PPS if:

- **Subject is randomized and did not satisfy certain eligibility criteria:**

- Subject presenting no diagnosis of MS as defined by the revised (2010) McDonald Diagnostic Criteria for MS or with no relapsing course from onset (no diagnosis of RRMS or SPMS with superimposed relapses) [PD_PP.013];
- No active disease as required per study protocol inclusion criterion 5 [PD_PP.014];
- Diagnosis of MS with progressive course from onset (i.e., diagnosis of primary progressive MS or progressive relapsing MS) [PD_PP.047];
- Treatment within 90 days prior to randomization with medication listed in study protocol exclusion criterion 8 [PD_PP.024], medications: Plasmapheresis, cytapheresis, i.v. immunoglobulin, Treatment with an investigational drug (within 90 days or five half-lives of the drug, whichever is longer), except biological agents;
- Treatment within 180 days prior to randomization with medication listed in study protocol exclusion criterion 9 [PD_PP.025], medications: Azathioprine, methotrexate, or cyclophosphamide, Natalizumab, Other systemic immunosuppressive treatment (e.g., cyclosporine, sirolimus, mycophenolic acid), Non-lymphocyte-depleting experimental biological agents (e.g., daclizumab);
- Treatment within 24 months prior to randomization with lymphocyte-depleting biological agents (e.g. rituximab or ocrelizumab) or cladribine [PD_PP.026];
- Treatment at any time prior to randomization with alemtuzumab, mitoxantrone, leflunomide, teriflunomide, fingolimod, ponesimod or other investigational S1P modulators, stem-cell transplantation [PD_PP.027];

- **Subject received no treatment or did not comply with treatment:**

- No treatment taken: Any randomized subject who never received study drug [PD_MM.175] is excluded from the Per Protocol Set;
- Compliance < 80 %, as per compliance based on days on study drug, derived from the eCRF, as described in Section 5.3.2.1, is excluded from the Per Protocol Set

Data will be excluded from the per protocol analysis for subjects after the occurrence of one of the following criteria:

- **Subject received wrong study treatment or incorrect dose:**

- Wrong study treatment taken for > 14 days (> 2 consecutive kits as one kit contains 7 doses): Derived as protocol deviation ‘Study drug taken from a non-allocated kit’ [PD_MM.058] and only applies if at least 2 non-allocated kits containing wrong treatment (derived at unblinding: PD_MM.0581) have been taken, exclusion from first intake start date + 14 days onwards. *Note: Wrong study*

treatment taken for ≤ 14 days is not expected to affect efficacy considerably based on pharmacodynamic profile of the study treatment.

- Premature treatment discontinuation: Any randomized subject with premature treatment discontinuation, derived from the eCRF, as described in Section 5.1.5, exclusion from EOT + 7 days onwards.
- **Subject took an unauthorized concomitant medication:**
 - Treatment with systemic corticosteroids and ACTH during treatment, except for MS relapses and short-term treatments with low dose/inhaled corticosteroids for pulmonary conditions defined in study protocol [PD_MM.087], from date of protocol deviation onwards;
 - Any administration of disease modifying therapy for MS during the treatment period [PD_MM.088, PD_MM.093], exclusion from medication start date onwards;
 - During treatment period, any investigational procedure for MS [PD_MM.096], from date of procedure onwards;
- **Occurrence of major protocol deviation that could confound the interpretation of analysis conducted on the FAS;**
 - EDSS assessments not conducted for more than 6 months, exclusion from ‘last EDSS date prior to 6-month gap + 6 months’ onward; derived from eCRF: time between two consecutive EDSS assessments (or last EDSS assessment and EOS date) is > 6 months (182 days).
 - Subject’s randomized treatment allocation was unblinded. Treatment code broken before unblinding of the study (for a reason not related to management of a clinical event [PD_MM.054], or any other unblinding documented in the IRT/eCRF), exclusion from date of unblinding onwards.

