1. For all post-baseline EDSS assessments (scheduled or unscheduled) assess if the absolute change from baseline meets the EDSS increase criteria for disability accumulation, described above. Start with the first EDSS assessment that meets the criteria for EDSS increase. Onset date of the corresponding potential 12-week CDA is the EDSS assessment date.

2. Confirmation of EDSS increase:

a. An EDSS increase of a potential 12-week CDA has to be confirmed by an EDSS increase at a scheduled visit, at least 70 days*, from the onset date of the potential 12-week CDA.

* Note: As visits are scheduled every 12 weeks with a time window of ± 7 days for conducting the EDSS assessment, the minimum per-protocol allowed time difference between two EDSS assessments scheduled 12 weeks apart is 70 days (12 weeks = 84 days minus a 7-day visit time window for each of the 2 visits, i.e., 84 days – 14 days = 70 days).

EDSS assessments conducted during a relapse, i.e., from relapse start date (inclusive) to minimum of relapse end date and relapse start date + 90 days (exclusive) are not considered for confirmation.

If an EDSS increase cannot be confirmed due to no available EDSS assessment, but the subjects dies due to MS (experiences a relapse with outcome death, or death with reason ‘Multiple sclerosis’) the CDA is also considered confirmed, with confirmation date being the death date and onset date the initial EDSS increase.

b. A confirmed EDSS increase as per (a) is considered persistent if every EDSS score available (scheduled or unscheduled) between the onset and the confirmation date of a potential 12-week CDA meets the EDSS increase criteria. The initial EDSS increase is considered a 12-week CDA.

If any EDSS from onset to confirmation does not meet the EDSS increase criteria, the increase is not persistent and the initial EDSS increase is not considered a 12-week CDA.

3. Repeat step 2 for all EDSS assessments with an EDSS increase as per the criteria above for disability accumulation, starting with the first possible onset, by date, up to the last possible onset. Once a 12-week CDA is identified the algorithm can stop.

4. If at none of the assessments a 12-week CDA is identified, but the subject dies due to MS (experiences a relapse with outcome death) the subject is considered to have a 12-week CDA with onset date being the death date.

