1.4. Exclusion criteria

Condition	Type	Identifier	Source/Instructions	Additional information expected?	Important PD
Lactating or pregnant woman	P	PD_PP.018	eCRF		Yes
Subject wishing to parent a child during the study	P	PD_PP.019	eCRF		Yes
Evidence of a relapse of MS with onset date < 30 days prior to baseline EDSS or between baseline EDSS and randomization	P	PD_PP.020	eCRF		Yes
Diagnosis of MS with progressive course from onset (i.e. diagnosis of primary progressive MS or progressive relapsing MS)	P	PD_PP.047	eCRF		Yes
Treatment within 7 days prior to randomization with IFN b-1a, IFN b-1b or glatiramer acetate	P	PD_PP.021	eCRF		Yes
Treatment within 15 days prior to randomization with b-blockers, diltiazem, verapamil, digoxin or any other anti-arrhythmic or HR lowering systemic therapy, cholestyramine or activated charcoal	P	PD_PP.022	eCRF		Yes
Treatment within 30 days prior to randomization with adrenocorticotrophic hormone (ACTH), systemic corticosteroids, dimethyl fumarate or vaccination with live vaccines	P	PD_PP.023	eCRF		Yes
Treatment within 90 days prior to randomization with medication listed in study protocol exclusion criterion 8	P	PD_PP.024	eCRF		Yes
Treatment within 180 days prior to randomization with medication listed in study protocol exclusion criterion 9	P	PD_PP.025	eCRF		Yes

	TPL-100062 Protocol Deviation Code List
Protocol Number: AC-058B301 Acronym: OPTIMUM	

Treatment within 24 months prior to randomization with lymphocyte-depleting biological agents (e.g. rituximab or ocrelizumab) or cladribine	P	PD_PP.026	eCRF	Yes
Treatment at any time prior to randomization with alemtuzumab, mitoxantrone, leflunomide, teriflunomide, fingolimod, ponesimod or other investigational S1P modulators, stem-cell transplantation	P	PD_PP.027	eCRF	Yes
Any infection or infection risk as per exclusion criteria 12, 13 and 14	P	PD_PP.028	eCRF	Yes
Known Progressive Multifocal Leukoencephalopathy (PML) infection / evidence of new neurological symptoms / MRI signs within 6 months prior to randomization compatible with a PML infection diagnosis	P	PD_PP.110	eCRF	Yes
Any malignancy as per exclusion criteria 15 and 16	P	PD_PP.029	eCRF	Yes
Presence of macular edema	P	PD_PP.030	eCRF	Yes
Any cardiovascular condition as per exclusion criterion 18	P	PD_PP.031	eCRF	Yes
Type 1 or 2 diabetes poorly controlled according to investigator's judgment, or diabetes complicated with organ involvement such as nephropathy or retinopathy	P	PD_PP.032	eCRF	Yes

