2.4. Efficacy / Endpoint

	TPL-100062 Protocol Deviation Code List
Protocol Number: AC-058B301 Acronym: OPTIMUM	

Condition	Type	Identifier	Source/Instructions	Additional information expected?	Important PD
Any scheduled EDSS assessment not done	M	PD_MM.185	eCRF / Monitor PD		No
Any EDSS assessment not performed as per study protocol (impact on validity of EDSS score)	M	PD_MM.190	eCRF / Monitor PD / Any deviation not matching to codes: PD_PP.097, PD_MM.134, PD_MM.185 or PD_MM.191; To be reviewed by GCS&E for coding to either PD_MM.190 or PD_MM.161		Yes
Any EDSS assessment not performed as per study protocol (no impact on EDSS score validity)	M	PD_MM.161	eCRF / Monitor PD / Any deviation not matching to codes PD_MM.097, PD_MM.134, PD_MM.185 or PD_MM.191; To be reviewed by GCS&E for coding to either PD_MM.190 or PD_MM.161		No
No EDSS assessment performed to confirm relapse	M	PD_MM.134	eCRF / Monitor PD		Yes
EDSS assessment confirming relapse performed > 7 days after onset of symptoms	P	PD_PP.097	eCRF		No
EDSS for unconfirmed relapse performed after start of treatment with steroids or > 7 days after onset of symptoms	M	PD_MM.191	eCRF / Monitor PD		Yes
FSIQ-RMS symptoms or impact domain not assessable at any given visit or FSIQ-RMS impact domain not assessable at Week 108 (Visit 14 or 14A)	M	PD_MM.163	Monitor PD / e.g., symptoms domain not completed or completed less than 4 days, impact domain not completed; For CDDM only: to be coded once		No
During treatment period or PTOP, any MRI missing or not performed as per study protocol (except Week 108)	M	PD_MM.162	eCRF / Monitor PD / e.g., not repeated in case of MRI unacceptable as per central overread, missing sequences		No

	TPL-100062 Protocol Deviation Code List
Protocol Number: AC-058B301 Acronym: OPTIMUM	

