3.2. Efficacy / Endpoints

Condition	Type	Identifier	Source/Instructions	Additional information expected?	Important PD
FSIQ-RMS symptoms domain not assessable at Week 108 (Visit 14 or 14A)	M	PD_MM.176	Monitor PD / e.g., symptoms domain not completed or completed less than 4 days		No
Week 108 (Visit 14 or 14A) MRI not performed as per study protocol	M	PD_MM.177	eCRF /		Yes

	TPL-100062 Protocol Deviation Code List
Protocol Number: AC-058B301 Acronym: OPTIMUM	

			e.g., not done or not repeated in case of unacceptable quality as per central overread, missing sequences, done < 14 days after treatment with corticosteroids	
Visit 14 (EOT) was not performed within 7 days after study drug discontinuation for a subject who completed 108 week-treatment as per study protocol.	P	PD_PP.179	eCRF	No
Visit 14 (EOT) was not performed within 7 days after study drug discontinuation for a subject who prematurely discontinued study treatment	P	PD_PP.180	eCRF	No
Any applicable follow-up visit not performed as per study protocol	M	PD_MM.181	eCRF / Monitor PD / e.g. done out of time-window, full instead of abbreviated Follow-up 2	No
Visit 14 (EOT) was not performed for a subject who prematurely discontinued study treatment	M	PD_MM.206	eCRF	Yes
Visit 14 (EOT) was not performed for a subject who completed 108 week-treatment as per study protocol	M	PD_MM.207	eCRF	Yes
Any applicable follow-up visit not performed	M	PD_MM.208	eCRF	Yes

4. Anytime during the study

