4.2. Efficacy / Endpoints

Condition	Type	Identifier	Source/Instructions	Additional information expected?	Important PD
Any EDSS assessment performed by personnel not qualified or not trained and certified or re-certified	M	PD_MM.049	eCRF / Monitor PD / "Neurostatus e-Test" web-based interactive test not passed or not re-certified as per protocol		Yes
Any ophthalmology related EDSS assessment not performed by the efficacy assessor	M	PD_MM.160	Monitor PD / For CDDM only: to be coded once		No
Any relapse assessment not performed as per study protocol anytime during the study	M	PD_MM.168	eCRF / Vendor data / Monitor PD / Includes: - scheduled calls for relapse detection not done - any of the following assessments for relapse detection not done: Relapse Assessment Questionnaire, Symptoms form, Body temperature, Physical exam		No
Any QoL questionnaire not performed or performed but with one or more question missing	M	PD_MM.126	Vendor data / Monitor PD / For CDDM only: to be coded once		No
Any MSFC/SDMT tests missing or not done as per study protocol	M	PD_MM.171	eCRF / Monitor PD / Includes: two PASAT alternate forms (i.e. A and B) not administered in a counterbalanced way across visits (< 40% of one type), incorrect sequence of tests, tests not timed; For CDDM only: to be coded once		No

	TPL-100062 Protocol Deviation Code List
Protocol Number: AC-058B301 Acronym: OPTIMUM	

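### The per-protocol rules in SAP Section 7.1.3 have no criterion for invalid EDSS scores, so scores the deviation list itself codes as affected in validity, and baselines scored soon after a relapse onset, stay in the per-protocol CDA analyses

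*SAP*

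**What the plan says.** **Definition.** SAP Section 7.1.3 bases the PP analysis on FAS data free of major deviations, and says: "Major protocol deviations are defined as protocol deviations that impact the assessment of the primary/secondary endpoints".

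**What is removed.** Two lists follow.
- Whole subjects are removed for no treatment, for compliance below 80%, or under the item "Subject is randomized and did not satisfy certain eligibility criteria", which names seven codes: PD_PP.013, .014, .024, .025, .026, .027 and .047.
- Later data are removed under the sentence "Data will be excluded from the per protocol analysis for subjects after the occurrence of one of the following criteria". The criteria are wrong kits, premature discontinuation, prohibited corticosteroids, disease-modifying therapy or procedures, an EDSS gap of more than 182 days, and unblinding.

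**Deviation code list.**
- Section 2.4 has PD_MM.190: "Any EDSS assessment not performed as per study protocol (impact on validity of EDSS score". Its instructions send each such case to review, to be coded either here or to PD_MM.161, which is for deviations that leave the score valid.
- Section 1.4 has PD_PP.020: "Evidence of a relapse of MS with onset date < 30 days prior to baseline EDSS or between baseline EDSS and randomization".

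**Derivations.** The PP variables for ARR (5.4.1.2.4), 12-week CDA (5.4.2.3.2.1) and 24-week CDA (5.4.2.4.2.1) use data up to the first deviation that 7.1.3 recognises. Section 5.4.2.3.1 takes as baseline the last EDSS on or before randomization. It does not accept a score taken during a relapse as confirmation of CDA, with the relapse capped at 90 days from onset. Section 9.6.5.2 gives the PP ARR analysis the task of showing whether major deviations biased the FAS result.

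**The concern.** The definition and the list under it do not agree. A deviation recorded as affecting the validity of an EDSS score meets the definition, because EDSS is the whole of the CDA endpoints and feeds relapse confirmation. It nevertheless triggers no exclusion.

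This matters most for CDA. The derivation is strict about single scores: "If any EDSS from onset to confirmation does not meet the EDSS increase criteria, the increase is not persistent". One wrong low score can cancel an event and one wrong high score can complete one. A baseline raised by a recent relapse lifts the threshold for every later visit. If PP CDA then agrees with the FAS result, that agreement says nothing about these data, because both analyses contain them.

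**Working it through.** There is no planned figure to reproduce. The check sets the lists side by side and then runs the CDA rule on illustrative scores.

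1. **Does PD_MM.190 meet the definition?** Yes, on its own wording. The review step that separates it from PD_MM.161 means the sponsor has already judged which EDSS deviations affect the score.

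2. **Is it in 7.1.3?** No. The only EDSS item is the gap of more than 182 days, which concerns visits without a score. The group holding that item has a general heading about confounding deviations, but only two entries are specified under it: the gap and unblinding. PD_PP.020 is not among the seven eligibility codes.

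3. **Is there a filter elsewhere?** No. The PP derivations for ARR and both CDA endpoints refer back to 7.1.3 and add no validity rule.

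4. **What can one score do?** Assume baseline 3.0, so the criterion is 3.0 + 1.0 = 4.0. Nominal days for Weeks 24, 36 and 48 are 169, 253 and 337 (Table 9). Confirmation needs at least 70 days for 12-week CDA and at least 154 days for 24-week CDA.
   - *Cancelling.* Scores are 4.0, 3.0 (invalid), 4.0. With the Week 36 score kept, the Week 24 onset is not persistent. With it set to missing, Week 48 confirms at 337 − 169 = 168 days, which satisfies both 70 and 154. The subject has a 12-week and a 24-week event with onset at Week 24.
   - *Creating.* Scores are 4.0, 4.0 (invalid), 3.0. With the Week 36 score kept, it confirms a 12-week event at 253 − 169 = 84 days. With it set to missing, the next scheduled score is 3.0 and the Week 24 onset gives no event.

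5. **What can the baseline do?** Assume a usual EDSS of 3.0 and a baseline of 4.0 scored in a relapse. An event needs 4.0 + 1.0 = 5.0, which is 5.0 − 3.0 = 2.0 above the usual level instead of the intended 1.0. A relapse that began less than 30 days earlier lies inside the 90-day cap. Unless it had already ended, the SAP would refuse a post-baseline score taken at that point as confirmation of CDA, yet it accepts one as baseline.

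6. **Relapses.** Under 5.4.1.1, confirmation status is collected for relapses with a completed EDSS. An EDSS coded PD_MM.190 can therefore support a confirmed relapse in PP ARR.

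**The case against.** Several points on the other side are sound and limit the finding.

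- **Important is not the same as major.** Section 6 and Section 7.1.3 use separate labels. PD_MM.175 (never treated) is flagged not important yet excludes the subject. A reader might infer that every important endpoint deviation should trigger PP exclusion; the SAP does not say so. The argument here rests only on the 7.1.3 definition.
- **The bias-check purpose is stated for ARR only.** PP CDA is a repeat of the main analysis with no stated purpose, so it cannot be faulted for failing one. The 7.1.3 definition does, however, cover the secondary endpoints.
- **Relapse confirmation is partly covered.** Section 9.6.5.3 analyses all relapses, a count that a wrong confirmation does not change. Section 9.6.5.5 handles missing confirmation status. Neither reaches CDA.
- **PD_PP.020 has two parts.** For a relapse between the baseline EDSS and randomization, the baseline precedes the relapse and is not raised by it. The deviation also occurs before randomization, so no difference between arms is expected.
- **Deviations are tabulated by arm** (9.3.2), so an imbalance would be visible, though its effect on the endpoint would not.

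Two wider readings are tempting and not supported. PD_MM.049, "Any EDSS assessment performed by personnel not qualified or not trained and certified or re-certified", also covers raters who were merely not re-certified. It does not say that the score is affected, and PD_MM.190 exists for that. PD_MM.177 gives as an example a Week 108 MRI "done < 14 days after treatment with corticosteroids", but it also covers scans not done, where there is nothing to remove. Section 5.4.2.2 expects CUAL to be driven mainly by new T2 lesions, so an effect of such scans on CUAL is not shown. Leaving these two codes out of 7.1.3 is not established as an error.

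**Conclusion.** The inconsistency is real and narrow. By its own definition Section 7.1.3 should act on EDSS scores coded PD_MM.190, and it does not. It also leaves in PP CDA those subjects whose relapse began less than 30 days before the baseline EDSS, which sits badly with the SAP's refusal of relapse-time scores for confirmation.

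For one subject the effect can be decisive, as the examples show. Those examples are assumed scores, not data. For the trial the size is unknown, because the documents give no count of these deviations. The primary analysis, the FAS analyses of the secondary endpoints and the alpha allocation are untouched, so severity is minor. It would be too strong to conclude that the PP analyses are uninformative or that the main result is biased. What follows is only that agreement between PP and FAS results is not evidence that invalid EDSS data did no harm.

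**What to change.** Add to Section 7.1.3, for the PP analyses only:

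- **CDA (12- and 24-week):** set EDSS scores coded PD_MM.190 to missing.
- **ARR:** treat a relapse confirmed only by such a score as unconfirmed. This can only lower the PP relapse count while follow-up time stays the same, so keep the all-relapse analysis in 9.6.5.3 as the companion check.
- **Baseline:** exclude from PP CDA, but not from the other PP analyses, subjects who fall under the first part of PD_PP.020.
- **Scope:** remove only the affected assessments and keep later data. Derive the 182-day gap from assessments as performed, so that setting a score to missing does not itself trigger the cut-off.

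If the sponsor prefers not to do this, narrow the definition in 7.1.3 and the purpose in 9.6.5.2 so that neither claims to cover invalid EDSS data.

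**Cost.** This is SAP wording plus programming. Deviation records must be linked to assessment dates. Section 7.1.3 already uses dates for other deviations, but the code list asks for no additional information under PD_MM.190, so the link has to be made. Slightly fewer data enter the PP analyses.

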Subjects who prematurely discontinue study treatment enter the PTOp period. It lasts from last dose of study drug until 108 weeks after randomization (i.e., end of planned treatment period) with 12-weekly visits as per the original visit schedule. Safety follow-up visits are conducted in addition, following the post-treatment safety follow-up period schedule.

Table 1 Dosing scheme

Treatment period	Duration	Dose regimen in the ponesimod group	Dose regimen in the teriflunomide group
Titration	Day 1 and 2	2 mg	14 mg
Titration	Day 3 and 4	3 mg	14 mg
Titration	Day 5 and 6	4 mg	14 mg
Titration	Day 7	5 mg	14 mg
Titration	Day 8	6 mg	14 mg
Titration	Day 9	7 mg	14 mg
Titration	Day 10	8 mg	14 mg
Titration	Day 11	9 mg	14 mg
Titration	Day 12 to 14	10 mg	14 mg
Maintenance	Day 15 until EOT*	20 mg	14 mg

*Visit 4 is to take place at Day 15 ± 1 day. The titration kit will therefore include an additional capsule and tablet (if applicable) for treatment on Day 15 (i.e., dose regimen in the ponesimod group = 10 mg). Dosing scheme during re-initiation following treatment interruption of > 3 days follows the same titration dosing scheme.
EOT = End-of-Treatment.

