As per protocol, one capsule of study drug is to be taken per day. On the ‘Maintenance Ponesimod/Teriflunomide’ eCRF log form, each record collects ‘Treatment start date’, ‘Treatment end date’, and ‘Number of capsules taken’. If, for a record, the ‘Number of capsules taken’ is \leq ‘Treatment end date’ – ‘Treatment start date’ + 1, it is assumed that the ‘Number of capsules taken’ represents the ‘Number of days with intake documented’ during that record’s period of study drug intake. If, for a record, the ‘Number of capsules taken’ is $>$ ‘Treatment end date’ – ‘Treatment start date’ + 1, ‘Number of days with intake documented’ is set to ‘Treatment end date’ – ‘Treatment start date’ + 1 for the compliance calculation. These subjects are flagged as having taken $>$ 1 capsule per day on at least one occasion.

The ‘Number of days with intake documented’ for a subject overall is derived as the sum across all study drug log records (sum across up-titration, or maintenance records; multiple periods of study drug intake during up-titration or maintenance are possible, e.g., due to interruptions, or detailed up-titration eCRF filled).

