2.6. Study drug

Condition	Type	Identifier	Source/Instructions	Additional information expected?	Important PD
Incorrect request of kit type via IVRS (i.e. up-titration kit instead of maintenance kit or vice-versa)	M	PD_MM.140	Vendor data / Monitor PD		Yes
Study drug taken from non-allocated kit	M	PD_MM.058	Vendor data / Monitor PD / e.g., incorrect kit dispensed, accidental exchange/ NB: PD to be classified after unblinding into the following two protocol sub-deviations: 'Study drug taken from non-allocated kit: non-assigned treatment received' (PD_MM.058.1) or 'Study drug taken from non-allocated kit: assigned treatment received' at unblinding (PD_MM.058.2)	Date of intake from incorrect kit (start and end date), kit number: (start date\end date\kit number)	Yes

		TPL-100062 Protocol Deviation Code List		
Protocol Number: AC-058B301				
Acronym: OPTIMUM				
During up-titration period, lack of compliance with study drug	P	PD_PP.055	eCRF / e.g., drug interrupted >1 day without re-up-titration, drug not taken in the correct sequence; For CDDM only: to be coded once per up-titration; to be raised manually in case of temporary interruption and no re-initiation	Yes
During up-titration period, at least one study drug dose not taken in the morning	M	PD_MM.120	Monitor PD / For CDDM only: to be coded once	No
IMP temperature excursion of any dispensed kit with GQM (GMP-DP) approval for use	M	PD_MM.156	Monitor PD / For CDDM only: to be coded once	No
IMP temperature excursion of any dispensed IMP kit without GQM (GMP-DP) approval for use	M	PD_MM.157	Monitor PD / To be reported for each affected subject	No
Misuse and abuse of study treatment	M	PD_MM.080	eCRF / Monitor PD / >3 doses taken on the same day	Yes
Study drug accountability and compliance check (if e-diary data available) was not performed at any applicable visit	M	PD_MM.059	Monitor PD	No
Subject did not return all used, partially used and unused study treatment blister packs at any given visit	M	PD_MM.060	Monitor PD	No
Any missing recording of study drug intake in the e-diary	M	PD_MM.057	Vendor data / Monitor PD / e.g., no record of more than 3 days at the time of study drug intake For CDDM only: to be coded once	No
Study drug not available at site in due time	M	PD_MM.192	Monitor PD / Valid for late IMP delivery causing any interruption	No
Overdose of study treatment	M	PD_MM.204	eCRF / Monitor PD / ≤3 additional doses taken	No

	TPL-100062 Protocol Deviation Code List

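### SAP 7.1.3 sets the wrong-treatment exclusion at more than 14 days but derives it from two or more kits, so 14 days or less can trigger the per-protocol cut

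*SAP*

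**What the plan says.** The SAP, section 7.1.3, lists the events after which a subject's data leave the per-protocol analysis. One bullet covers intake of the wrong drug and has four parts.

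- The criterion: "Wrong study treatment taken for > 14 days (> 2 consecutive kits as one kit contains 7 doses").
- The derivation, from deviation code PD_MM.058 (drug taken from a non-allocated kit): it "only applies if at least 2 non-allocated kits containing wrong treatment (derived at unblinding: PD_MM.0581) have been taken".
- The cut date: "exclusion from first intake start date + 14 days onwards".
- A note giving the reason for the tolerance: wrong "treatment taken for ≤ 14 days is not expected to affect efficacy considerably based on pharmacodynamic profile of the study treatment".

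Section 5.3.2.1 gives the maintenance dose frequency: "As per protocol, one capsule of study drug is to be taken per day". Section 5.4.1.2.4 then applies the cut to ARR. Relapses after the exclusion date are not counted, and observation time ends there.

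The attached Protocol Deviation Code List, section 2.6, shows what is collected with PD_MM.058: "Date of intake from incorrect kit (start and end date), kit number".

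**The concern.** The criterion and its derivation set different thresholds. The criterion needs more than two kits and needs them to be consecutive. The derivation is met at two kits and drops the second requirement. The note says that 14 days or less should matter little for efficacy, and section 7.1.3 defines a major deviation as one that affects assessment of the primary or secondary endpoints. On the plan's own terms, then, a subject with 14 days or less on the wrong drug has no major deviation, yet the derivation cuts that subject's follow-up.

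The exclusion date feeds the per-protocol analyses of ARR (sections 5.4.1.2.4 and 9.6.5.2), fatigue, CUAL and 12- and 24-week CDA, and the per-protocol ARR subgroup analyses (section 9.6.7). Section 9.6.5.2 uses the ARR analysis to judge whether major deviations have biased the FAS result. Removing follow-up that the plan considers unaffected works against that purpose.

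Timing also matters. Wrong-kit intakes are classified as non-assigned or assigned treatment only at unblinding (section 6). An unresolved threshold would therefore be settled when treatment codes are known.

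**Working it through.** **Inputs.** 7 doses per kit (section 7.1.3); 1 dose per day in maintenance (section 5.3.2.1); limit of more than 14 days, or more than 2 consecutive kits; derivation of at least 2 kits; cut at first wrong intake + 14 days (all section 7.1.3). Planned treatment is 108 weeks, or 756 days.

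**Step 1: the plan's own conversion.** Days = kits × 7.

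| Full wrong kits | Days | Criterion (> 14 days, > 2 kits) | Derivation (≥ 2 kits) |
|---|---|---|---|
| 1 | 7 | not met | not met |
| 2 | 14 | not met | **met** |
| 3 | 21 | met | met |
| 4 | 28 | met | met |

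The stated equivalence of more than 14 days with more than 2 kits reproduces. For full consecutive kits the derivation departs from it at exactly 2.

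**Step 2: what is dropped with two consecutive kits.** Let d be the study day of the first wrong dose. Wrong-drug days are d to d + 13. Data are excluded from d + 14, the first day back on assigned drug. All 14 wrong-drug days stay in. Days dropped to Day 756 = 756 − (d + 14) + 1. The values of d below are assumed.

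| First wrong dose, day d | Excluded from day | Days dropped | Share of 756 days |
|---|---|---|---|
| 15 | 29 | 728 | 96% |
| 85 (Week 12) | 99 | 658 | 87% |
| 169 | 183 | 574 | 76% |
| 421 | 435 | 322 | 43% |
| 673 | 687 | 70 | 9% |

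For the Week 12 row, 658 / 7 = 94 of 108 weeks. In every row all dropped days are on the assigned drug.

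**Step 3: two separated kits.** Assume wrong kits on days 15–21 and 315–321. Neither run exceeds 7 days and the total is 14. The derivation is still met, and the cut is dated from the first kit, at day 29. Days dropped = 756 − 29 + 1 = 728, of which 728 − 7 = 721 are on the assigned drug. Two part-used kits, totalling fewer than 14 days, meet the derivation in the same way.

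**Step 4: scale against the whole trial.** With 1133 randomised subjects (section 2), and assuming all are followed for 108 weeks, follow-up is 1133 × 108 = 122,364 subject-weeks. One subject losing 94 weeks removes 94 / 122,364 = 0.08%; ten would remove about 0.8%.

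**The case against.** The strongest defence is that the kit count is an added condition and not a replacement. The bullet opens with more than 14 days, the note repeats that limit, and the phrase about at least two kits may only narrow PD_MM.058 further. On that reading nobody with 14 days or less is cut. It does not fit the text well. With 7-dose kits, more than 14 days already needs a third kit, so a two-kit minimum would add nothing. The bullet also presents the kit count as how the criterion is derived. The defence does show that the outcome depends on which half of the bullet is followed. No code for this rule is shown, so a reader should not infer that the error has already been programmed.

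A reader might also blame the mismatch for the loss of all later data. That loss is the general design: section 7.1.3 removes data after any post-randomisation major deviation. A three-kit subject, excluded under both thresholds, also loses later follow-up on assigned drug. Only the trigger is at fault.

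It is tempting to add that a wrong titration kit escapes exclusion. The footnote to Table 1 says "The titration kit will therefore include an additional capsule and tablet (if applicable) for treatment on Day 15", so one kit could supply 15 days. But the criterion in days would capture 15 days, and the conversion "as one kit contains 7 doses" does not describe that kit. The supported point is only that the conversion does not fit it.

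Finally, the per-protocol analyses are supplementary and carry no alpha. The ARR offset is shortened together with the relapse count, so lost time is not treated as relapse-free. Both points stand and limit the importance of the problem.

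**Conclusion.** The inconsistency is real, and nothing elsewhere in the SAP reconciles it. Followed as derived, the rule cuts subjects with exactly two wrong kits, and those with separated or part-used kits that do not amount to more than 14 days. The plan's own note gives no ground for cutting them.

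The reach is limited. The main analyses of the primary and secondary endpoints use the FAS and do not change, so the documents do not support any inference that the trial's main conclusions are at risk. The SAP does not say how many subjects took two or more wrong kits; the number is probably small. The 94 of 108 weeks is one hypothetical subject's loss under an assumed Week 12 start, and is not an estimate of the effect on any analysis. The arithmetic assumes full kits taken once daily, except where part-used kits are named.

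The point still merits correction, because an exclusion threshold should have one meaning before treatment codes are opened.

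**What to change.** Make the derivation in section 7.1.3 match its criterion before unblinding. Either of two changes would do it.

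1. **Minimum change.** State more than two consecutive kits of non-assigned treatment in both places.
2. **Preferred.** Derive the duration from the intake start and end dates recorded with PD_MM.058 (sub-class PD_MM.0581). Exclude data only after more than 14 consecutive days of non-assigned treatment, from day 15 of that run onwards, whatever the number or type of kits.

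The first restores consistency for 7-dose kits. The second also handles part-used kits and avoids applying the 7-dose conversion to the titration kit. The cost is one sentence in the SAP and, for the second option, a short date-based derivation. No new data are needed.
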